1.1 Background

Short bowel syndrome (SBS) is a malabsorption disorder that manifests as a collection of signs and symptoms such as diarrhea, steatorrhea, fluid and electrolyte disturbances, dehydration, malnutrition, and weight loss. Short bowel syndrome typically develops after loss of more than two-thirds of the small intestine, e.g., through surgical resection of the bowel secondary to Crohn's disease, mesenteric vascular complications, trauma or necrotizing enterocolitis. Short bowel syndrome intestinal failure (IF) is defined by the inability to maintain protein, energy, fluid, electrolyte, or micronutrient balance, and patients with SBS-IF are dependent on intravenous fluids, electrolytes and/or nutrients, together termed parenteral support (PS) [4]. Other patients present a less severe form of SBS defined as intestinal insufficiency (II), characterized by a remnant small intestine of 200 cm or less, a fecal energy excretion of more than 2.0 MJ/day, or consecutive small intestinal resections exceeding 150 cm [5]. Generally, SBS-II patients can maintain their protein and energy balance through hyperphagia, but some of them are considered as borderline IF patients with a high risk to require intermittent PS.

Following surgical resection, the remaining small intestine may undergo a process of structural and functional adaptation, which may lead to restoration of intestinal secretion and motility and to hypertrophy and hyperplasia of the mucosal surface. In patients with a preserved terminal ileum or colon in continuity, an increase in the endogenous hormonal secretion of the peptide hormones glucagon-like peptide-1 (GLP-1), GLP-2, and peptide YY (PYY) following nutrient ingestion may play a role in this adaptation. However, for patients with resection of the ileum and colon, these neuroendocrine feedback mechanisms are disrupted which may be associated with the pathophysiological traits in SBS patients such as accelerated gastrointestinal (GI) motility, hypersecretion, diminished GI blood flow, and disturbed barrier function. Together these observations have led to the development and pharmacological use of GLP-2 in the intestinal rehabilitation and treatment of SBS patients [6].

Glucagon-like peptide-2 is a 33-amino acid peptide derived from posttranslational processing of proglucagon in intestinal L-cells located primarily in the terminal ileum and colon [7, 8]. GLP-2 and GLP-2 receptor agonists act in a highly localized manner in the GI tract to enhance nutrient and fluid absorption, stimulate blood flow, increase intestinal barrier function, and inhibit gastric acid secretion and gastric emptying. One of the main biological actions of GLP-2 is organ-specific stimulation of intestinal growth through increased crypt cell proliferation and decreased apoptosis of the mucosal epithelial cells [6, 7]. Data from previous clinical trials with native GLP-2 and GLP-2 analogues have demonstrated that GLP-2 supplementation has the ability to increase crypt depth and villus height [9, 10, 11] and enhance the intestinal absorptive capacity in patients with SBS [9, 10, 11, 12].

Apraglutide is a peptide analogue of GLP-2, which is under development for the treatment of SBS. Apraglutide acts as a full agonist at the GLP-2 receptor *in vitro* with potency and selectivity comparable to native GLP-2 [8]. The structure of this peptide is designed to have a longer elimination half-life by being resistant to cleavage by dipeptidyl peptidase-4 (DPP4), the major GLP-2 peptidase. The systemic half-life in various animal species as well as in human healthy subjects is significantly prolonged compared with the native human GLP-2 (approximately 30 hours when administered subcutaneously [SC] vs 7 minutes for native GLP-2). Apraglutide has, in various animal models, shown

a trophic effect on the small intestine and maintained the barrier function, thus preserving the physical integrity of the intestinal mucosa.

In previous nonclinical pharmacokinetics and metabolism trials, no intact parent compound (apraglutide) was found in urine, suggesting renal elimination does not play a significant role in apraglutide removal.

Previously, apraglutide has been administered in a first-in-human trial with healthy subjects to assess safety and determine pharmacokinetic (PK) characteristics, and proved safe and well tolerated at single and repeated SC doses ranging from 2.5 mg up to 25 mg. In humans, again, no intact parent compound (apraglutide) was found in urine suggesting renal elimination does not play a significant role in apraglutide removal in humans.

1.2 Rationale

This trial is a Phase 1, non-randomized, open-label, single dose, parallel-group trial of apraglutide in subjects with severe renal impairment and subjects with normal renal function (Part 1) and in subjects with mild and moderate renal impairment (Part 2) matched for age and body weight. Details on the age and body weight matching criteria are specified in Section 4 of the protocol.

Since the metabolic pathway of apraglutide is expected to be degradation into small peptides and amino acids via catabolic pathways, similar to the catabolism for endogenous GLP-2, and in keeping with previous nonclinical and clinical pharmacokinetic trials that demonstrated no intact parent compound being recovered from the urine, it is not expected that renal impairment will have an impact on the PK of apraglutide. Therefore, a reduced, adaptive trial design will be pursued. In this trial design, only subjects with severe renal impairment and normal renal function will be studied first. In this manner, the effect of renal impairment on apraglutide PK will be initially evaluated in the renal impaired population most likely to be of impact. The impact of renal impairment expression of cytochrome P450 (CYP) enzymes, if any, is expected to be minimal and hence can also be evaluated in the severely renally impaired population to estimate degree of impact. If the trial results confirm that severe renal impairment does not alter PK to an extent that warrants dose adjustment, no further trial is warranted. If the results do not support such a conclusion, Part 2 will be conducted in subjects with moderate and mild renal impairment, based on the decision criteria outlined in Section 3.

Single-dose of SC apraglutide PK appears to be linear in the dose ranges between 2.8 mg to 56.9 mg relative to C_{max} and AUC_{inf} . No direct enzyme inhibition/induction or time-dependent enzyme inhibition is expected. The absolute bioavailability was 24.6% and the terminal half-life ($t_{1/2}$) was approximately 30 hours. Considering a linear PK at the therapeutic dose range being tested in Phase 2 trials (5–10 mg) in which single-dose PK behavior can predict multiple dose PK, a single-dose trial will be conducted to evaluate apraglutide PK under conditions of renal impairment.

The trial will use a single dose of 5 mg apraglutide administered via SC injection.

1.3 Risk-benefit Assessment

The overall conclusion from the nonclinical and Phase 1 and 2 trials conducted with apraglutide is that there are no apparent safety concerns with the administration of apraglutide in the 5 mg dose selected for this trial. A single dose of 56.9 mg was safe and well tolerated in the single ascending dose (SAD)

part of the entry into human trial. The selected dose of 5 mg is expected to produce exposures well below the levels previously found to be safe and well tolerated, even accounting for some increase in renally impaired subjects. Current data indicate that apraglutide has intestinotrophic effects on the intestinal epithelium, which may result in transient abdominal side effects.

In the following sections, the current nonclinical and clinical experience with apraglutide is summarized. A detailed review of pre-clinical and Phase 1 results is provided in the Investigator's Brochure.

1.3.1 Nonclinical Experience

1.3.1.1 Pharmacokinetics

Nonclinical trials of apraglutide have been conducted in mice, rats, monkeys and minipigs.

The PK properties of apraglutide, administered at various dose levels either intravenously (IV) as a single bolus or by SC injection, were found to be consistent across species with no apparent sex differences. The PK profile was characterized by a low systemic clearance, small volumes of distribution, and a long half-life when compared to human GLP-2 and other known GLP-2 agonists. Following SC administration, apraglutide displayed absorption-controlled kinetics resulting in a protracted half-life being 5–6 times longer compared to the half-life after IV administration. It is believed that the low clearance and the long half-life depend, at least in part, on the high protein binding and slow metabolism of the drug.

1.3.1.2 Safety

Single-, 2-week and 5-week repeated dosing trials in rats and minipigs showed dose-related mucosal effects (hyperplasia and hypertrophy of intestinal villi and crypts) of apraglutide in the intestine of both species, demonstrating the expected mode of action of the compound and the responsiveness of both animal species to the treatment.

When the intestinal mucosa was examined by standard histology, morphometry or immunohistochemistry for proliferation and apoptosis, no adverse forms of cell growth, e.g., aberrant cell division, pre-neoplastic or neoplastic changes, excessive apoptosis or cell necrosis were revealed. Moreover, additional investigation conducted *in vitro* using 50 tumor cell lines, including several colon cancer cell lines, showed that the expression of the GLP-2 receptor mRNA in the large majority of these cell lines is extremely low (100-fold to >1000-fold lower) when compared to the expression of the GLP-2 receptor mRNA of the positive controls. Therefore, the pharmacologic profile of apraglutide was found to be consistent with a minimal risk of direct action to stimulate proliferation of tumor cells or the release of growth factors from tumor cells.

Data from the pivotal toxicology *in vivo* trials (5-week repeated treatment) also indicated that apraglutide was not immunogenic in the selected animal species, had no dose-limiting or adverse systemic changes, and no effect on the respiratory, cardiovascular or nervous systems. Apraglutide did not induce genotoxicity when tested using *in vitro* or *in vivo* assays and did not have effects on reproductive organs with regard to clinical behavior, weight of the organs or macroscopic/microscopic examination.

Regarding local tolerance, investigation in the minipig found a presumably concentration-dependent local irritating potential of the dose formulations that were considered to be of human relevance. The degree of local irritation observed, however, was minimal to slight and similar to the vehicle control.

1.3.2 Clinical Experience

To date, 104 subjects participated in four clinical trials with apraglutide among whom 82 subjects (66 healthy subjects and 16 SBS patients) received at least one dose of apraglutide. These four completed clinical trials are described below:

- Two Phase 1 clinical trials in healthy subjects:
 - Clinical trial GYM-P3-698, a single-ascending dose (SAD) and multiple-ascending dose (MAD), placebo-controlled clinical trial of apraglutide in healthy adult subjects evaluating safety, tolerability, PK, and PD
 - Clinical trial TA799-002, a multiple-dose parallel arm clinical trial in healthy adult subjects to evaluate the effect of multiple SC doses of either apraglutide (1, 5, or 10 mg) or placebo once weekly for 6 weeks on the PD marker citrulline
- Two Phase 2 clinical trials designed to assess the safety and tolerability and to demonstrate proof-of-concept for apraglutide in SBS subjects:
 - Clinical trial GLY-321-2017, an open label metabolic balance clinical trial in SBS subjects testing a weekly dose of 5 mg apraglutide in SBS patients
 - Clinical trial GLY-311-2017, a dose-exploration clinical trial in SBS-IF subjects testing weekly 5 mg apraglutide against placebo and 10 mg apraglutide in an open-label extension

1.3.2.1 Pharmacokinetics

Dose-proportional PK parameters obtained by non-compartmental analysis were seen after multiple doses for apraglutide within the range of 5.7 mg to 56.9 mg in clinical trial GYM-P3-698 and within the range of 1 mg to 10 mg in clinical trial TA799-002.

A population PK/PD model of apraglutide in healthy subjects and SBS patients [13] has been developed with data provided by the 82 subjects exposed to apraglutide to date. This model describes well apraglutide concentrations across the whole-body weight range of the subjects and for the doses of 1 to 50 mg SC with one central compartment with zero-order absorption from the subcutaneous administration site and first order elimination from the central compartment. The typical PK parameters for a 70 kg-weight human receiving 5 mg are:

- Absorption duration: 1.46 days
- Apparent volume of distribution: 31.5 L
- Clearance: 16.8 L/day
- Half-life: 1.32 days

The inter-individual variability (% coefficient of variation [CV]) was 35% on clearance and 41% on the volume of distribution. Body weight influenced clearance and the volume of distribution. No

statistically significant difference was found between the PK parameters of healthy subjects and SBS patients.

Body weight was found to be a covariate on clearance and apparent volume of distribution.

1.3.2.2 Pharmacodynamics

Apraglutide increased plasma citrulline levels (a surrogate marker of small intestine enterocyte mass and function) and increased intestinal absorption as demonstrated by the following:

In clinical trials GYM-P3-698 and TA799-002, plasma citrulline levels increased in a dose dependent manner reaching a plateau at approximately 10 mg.

In the metabolic balance clinical trial GLY-321-2017, apraglutide at a weekly dose of 5 mg increased intestinal absorption after 4 weeks of treatment, as evidenced by increased wet weight absorption, energy absorption, and urinary output in SBS patients.

The results seen with apraglutide in the dose-exploration clinical trial GLY-311-2017 are consistent with those seen in the metabolic balance clinical trial GLY-321-2017. Apraglutide increased urinary output, a surrogate marker of intestinal absorption. No statistically significant difference between 5 mg and 10 mg doses was observed.

1.3.2.3 Safety

Apraglutide has been generally safe and well tolerated in the clinical studies conducted to date as demonstrated by the following:

- Doses up to 56.9 mg were safe and well tolerated in the SAD and MAD parts of the Phase 1 clinical trial GYM-P3-698
- Apraglutide was well tolerated up to six weekly doses of 10 mg in clinical trial TA799-002 in healthy subjects
- A dose relationship has not been seen for any adverse event (AE) in any of the studies
- The most frequent AEs in clinical trial GLY-321-2017 included nausea, GI stoma output decreased, and stoma complications
- Frequent AEs in clinical trial GLY-311-2017 were primarily related to the expected PD effects of apraglutide, including decreased stoma output or stoma output abnormal, polyuria, and decreased thirst
- Serious AEs (SAEs) have primarily been disease complications that are common in SBS subjects, including device-related sepsis and device malfunction. Two subjects had three treatment-emergent SAEs. All of the SAEs resolved; only one SAE, abdominal pain, was assessed by the Investigator as related to apraglutide
- For each hematology, coagulation, and chemistry parameter, mean and median change from baseline were not clinically significant. Isolated occurrences of clinically-significant, out-of-range laboratory parameters were reported as AEs, but there was no consistent pattern with the occurrence of these events
- No QTcF prolongation >500 milliseconds was seen in any of the clinical trials. In clinical trials GLY-311-2017 and GLY-321-2017, the changes from baseline in the QTcF values were

≤30 msec for all subjects at all time points, except for one subject at the EOT visit and in another subject at pre-dose of Period 3

- Low-titer anti-drug antibodies (ADA) have been seen in five subjects (none in clinical trial GYM-P3-698, one in clinical trial TA799-002, three in clinical trial GLY-311-2017, and one in clinical trial GLY-321-2017). ADA had no apparent effect on either the PD or PK of apraglutide

2 Trial Objectives and Endpoints

2.1 Objectives

2.1.1 Primary Objective

- Part 1 of clinical trial: To assess the pharmacokinetics (PK) of apraglutide in subjects with severe renal impairment compared to matched control subjects with normal renal function following single SC dose administration
- Part 2 of clinical trial (if applicable; see criteria to move to Part 2 in Section 3.1.1): To assess the PK of apraglutide in subjects with moderate and mild renal impairment compared to matched control subjects following single SC dose administration

2.1.2 Secondary Objective

- To assess the safety and tolerability of apraglutide administered to subjects with varying degrees of impaired renal function

2.2 Endpoints

2.2.1 Primary Endpoints

- Plasma apraglutide PK parameters: C_{max} and AUC_{inf} , AUC_{last} , $AUC_{0-7days}$, T_{max} , λ_z , $t_{1/2}$, CL/F , V_z/F
 C_{max} and AUC_{inf} or AUC_{last} are primary PK parameters. All others as secondary PK parameters

2.2.2 Secondary Endpoints

- Adverse events (type, frequency and intensity), adverse events of special interest (AESIs), vital signs (systolic and diastolic blood pressure [BP], heart rate), recorded triplicate ECG (intervals, rhythm, and morphology), clinical chemistry, hematology and urinalysis

3 Overall Design and Plan of the Trial

3.1 Overview

This is a Phase 1, non-randomized, open-label, single-dose trial to evaluate the effect of varying degrees of impaired renal function on the PK, safety, and tolerability of apraglutide administered by subcutaneous injection in a clinical research unit (CRU). A staged approach as outlined will be followed in the trial.

Subjects will be selected and categorized into normal renal function or renal impairment groups based on their estimated glomerular filtration rate (eGFR) using the Chronic Kidney Disease Epidemiology (CKD-EPI) equation (Table 2).

Table 2: CKD-EPI Equation

Part 1

Cohort ^a	eGFR (mL/min/1.73 m ²) ^b	N
1 (Severe Renal Impairment)	<30 not on hemodialysis	8
2 (Normal Healthy Match)	≥90	8

Part 2

Cohort ^a	eGFR (mL/min/1.73 m ²) ^b	N
3 (Moderate Renal Impairment)	≥30 to <60	8
4 (Mild Renal Impairment)	≥60 and <90	8

^a Stages of Renal Impairment are based on the Kidney Disease Outcomes Quality Initiative (KDOQI) Clinical Practice Guidelines for Chronic Kidney Disease (CKD) [15].

^b Estimated glomerular filtration rate (eGFR) based on Chronic Kidney Disease Epidemiology (CKD-EPI). The baseline eGFR will be obtained by taking the mean of the eGFR obtained from screening and from historical values within a 3-month period from screening. If no historical measurement is available, a second baseline eGFR sample will be taken during the screening period (≥72 hours apart, but no more than 14 days apart) and the mean of the two values will be used for the group assignment; the second baseline eGFR sample may be obtained at the time of check-in. Subjects will be assigned to one of the 4 renal function groups based on eGFR values at screening. Estimated GFR will be calculated using the CKD-EPI Creatinine Equation [16]:

$$eGFR = 141 \times \min(SCr/\kappa, 1)^\alpha \times \max(SCr/\kappa, 1)^{-1.209} \times 0.993^{Age} \times 1.018 [\text{if female}] \times 1.159 [\text{if black}]$$

Notes: eGFR is expressed as mL/min/1.73 m² of body surface area, SCr (serum creatinine) is expressed in mg/dL

κ = 0.7 (females) or 0.9 (males)

α = -0.329 (females) or -0.411 (males)

[figure not shown]
min = indicates the minimum of SCr/ κ or 1

max = indicates the maximum of SCr/ κ or 1

age is in years

Reasonable efforts will be made to enroll at least two subjects with eGFR values of <20 mL/min/1.73 m²

Figure 1: Trial Schematic

CRU=clinical research unit; PK=pharmacokinetics; SC=subcutaneous

3.1.1 Part 1 of Clinical Trial

A total of approximately 16 subjects will be enrolled in Part 1; approximately eight subjects with severe renal impairment (Cohort 1) and approximately eight with normal renal function (Cohort 2) to ensure at least six evaluable subjects in each group. Subjects from the severe renal impairment group will be recruited first. The demographics will be pooled across enrolled subjects to determine an average value for age and weight in the severe impairment group. Subsequently, the healthy subjects will be recruited later such that each subject's age is within ± 10 years and weight is within ± 15 kg of the mean of the severe renal impairment group. Care will be taken when recruiting the healthy subjects such that the entire group is not of substantially different age or of substantially different body weight than the severely renally impaired subjects.

Criteria to proceed to Part 2: After evaluation from Part 1, Part 2 will be conducted if the point estimate of apraglutide area under the concentration-time curve from time 0 to infinity (AUC_{inf} or AUC_{last} [if AUC_{inf} cannot be calculated]) geometric mean ratio (GMR) for the severe renal impairment group (compared to the normal group as control) is ≥ 2 . This metric is supported by recommendations from Huang *et al* [14]. Furthermore, apraglutide was well tolerated up to 56.9 mg SC QW and very well tolerated at 28.4 mg SC QW, further demonstrating the large therapeutic margin of apraglutide. If this criterion is not met, the trial will stop after Part 1.

If there are subjects who withdraw or discontinue treatment from the normal or severe renal impairment groups and who are considered to be non-evaluable with respect to the primary PK objective, additional subjects can be enrolled at the discretion of the sponsor.

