8.3 Statistical Analysis

The Statistical Analysis Plan (SAP) will be developed and finalized prior to database lock. The SAP will describe the subject populations to be included in the analysis. Unless otherwise noted in SAP, missing values will not be imputed. An explanation will be given for any missing, unused, and spurious data affecting analysis in the relevant sections of the Clinical Trial Report (CTR). This section is a summary of the planned statistical analysis of the primary and secondary endpoints.

Part 1

Analysis of variance (ANOVA) will be used to compare the natural log transformed AUC_{inf} or AUC_{last} (if AUC_{inf} cannot be calculated) and C_{max} for apraglutide between normal renal function group (Reference) and the severe impaired renal group (Test). Estimates of the mean differences (Test-Reference) and corresponding 90% CIs will be obtained from the model. The mean differences and 90% CIs for the differences will be exponentiated to provide estimates of the ratio of the adjusted geometric means (Test/Reference) and 90% CIs for the ratios.

Part 2 may be conducted if apraglutide AUC_{inf} (or AUC_{last} when AUC_{inf} cannot be calculated) GMR for severe renal impairment group compared to normal group is ≥ 2.0 . This metric is supported by recommendations from Huang *et al* [14]. Furthermore, apraglutide was well tolerated up to 56.9 mg SC QW and very well tolerated at 28.4 mg SC QW further demonstrating the large therapeutic margin of apraglutide.

Part 2

Analysis of variance will be used to compare the natural log transformed AUC_{inf} or AUC_{last} and C_{max} for apraglutide between normal renal function group from Part 1 (Reference) and each of the moderate and mild impaired renal groups (Test). Estimates of the mean differences (Test-Reference) and corresponding 90% CIs will be obtained from the model. The mean differences and 90% CIs for the differences will be exponentiated to provide estimates of the GMR (Test/Reference) and 90% CIs for the ratios.

Box and whisker plots for individual subject parameters (AUC_{inf} or AUC_{last} and C_{max}) will be constructed by renal function group and overlaid with geometric means.

For summary statistics and median/mean plots by sampling time, the nominal PK sampling time will be used. For individual subject plots by time, the actual PK sampling time will be used.

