Part 1 of clinical trial: A total of approximately 16 subjects will be enrolled in Part 1: approximately eight subjects with severe renal impairment (Cohort 1) and approximately eight subjects with normal renal function (Cohort 2) to ensure at least six evaluable subjects in each group. Subjects from the severe renal impairment group will be recruited first. The demographics will be pooled across enrolled subjects to determine an average value for age and weight in the severe impairment group. Subsequently, the healthy subjects will be recruited later such that each subject's age is within ±10 years and weight is within ±15 kg of the mean of the severe renal impairment group. Attempts will be made to maintain a similar male/female ratio composition between groups. Care will be taken when recruiting the healthy subjects such that the entire group is not of substantially different age or of substantially different body weight than the severely renally impaired subjects.

Criteria to proceed to Part 2: After evaluation from Part 1, Part 2 will be conducted if the point estimate of apraglutide area under the concentration-time curve from time 0 to infinity (AUC_{inf}, or to the time of the last quantifiable concentration (AUC_{last}), if AUC_{inf} cannot be calculated) geometric mean ratio (GMR) for the severe renal impairment group compared to the control group (normal renal function group) is ≥2.

If criterion is not met, the trial will stop after Part 1. If there are subjects who withdraw or discontinue treatment from the normal or severe renal impairment groups and who are considered to be non-evaluable with respect to the primary PK objective, replacement subjects can be enrolled at the discretion of the sponsor.

Part 2 of clinical trial: If the decision criterion to proceed to Part 2 is met, approximately eight subjects each with moderate (Cohort 3) and mild (Cohort 4) renal impairment will be enrolled to ensure at least six

[figure not shown]
evaluable subjects in each group. As in Part 1, renal impairment classification will be based on eGFR. Healthy subjects will not be enrolled in Part 2. Healthy subjects from Part 1 will be used as the control group of the moderate and mild renal impairment subjects.

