16.2.2.1 Statistical Analyses

Part 1:

Analysis of variance (ANOVA) will be used to compare the natural log transformed AUCinf or AUClast (if AUCinf cannot be calculated) and Cmax for apraglutide between normal renal function group (Reference) and the severe impaired renal group (Test). Estimates of the mean differences (Test-Reference) and corresponding 90% CIs will be obtained from the model. The mean differences and 90% CIs for the differences will be exponentiated to provide estimates of the GMR (Test/Reference) and 90% CIs for the ratios.

The following SAS PROC MIXED pseudo-code may be used:

```
proc mixed data = adpp;
  by analyte parameter;
  class renal_group;
  model ln(aval) = renal_group;
  lsmeans renal_group / cl alpha = 0.1;
  estimate "Severe renal impairment vs Normal renal function" renal_group -1
  1 /e cl alpha=0.1;
run;
```

Part 2 (if conducted):

Analysis of variance will be used to compare the natural log transformed AUCinf or AUClast and Cmax for apraglutide between normal renal function group from Part 1 (Reference) and each of the moderate and mild impaired renal groups (Test). Estimates of the mean differences (Test-Reference) and corresponding 90% CIs will be obtained from the model. The mean differences and 90% CIs for the differences will be exponentiated to provide estimates of the GMR (Test/Reference) and 90% CIs for the ratios.

The following SAS PROC MIXED pseudo-code may be used:

```
proc mixed data = adpp;
  by analyte parameter;
  class renal_group;
  model ln(aval) = renal_group;
  lsmeans renal_group / cl alpha = 0.1;
```

```
estimate "Moderate renal impairment vs Normal renal function" renal_group  
0 -1 0 1 /e cl alpha=0.1;  
estimate "Mild renal impairment vs Normal renal function" renal_group 0 -1  
1 0 /e cl alpha=0.1;  
run;
```

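### Stopping after Part 1 is treated as confirming no dose-relevant PK change, but the test is a point estimate below 2 and the planned 90% CI has no role

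*Protocol*

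**What the plan says.** Protocol 1.2 Rationale describes a reduced, staged design. If Part 1 confirms that severe impairment "does not alter PK to an extent that warrants dose adjustment, no further trial is warranted". If the results do not support that conclusion, Part 2 follows, on the decision criteria given in Section 3.

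Protocol 3.1.1 gives those criteria: Part 2 "will be conducted if the point estimate" of the AUC GMR for the severe group ("compared to the normal group as control) is ≥ 2"). It then adds: "If this criterion is not met, the trial will stop after Part 1". The synopsis carries the same rule, as does SAP 6.0 ("compared to the control group (normal renal function group) is ≥2"). Protocol 8.3 repeats the threshold, with the softer verb *may* in place of *will*. None of these places sets a condition on the CI.

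The CI itself is planned. Protocol 8.3 says "The mean differences and 90% CIs for the differences will be exponentiated", and SAP 16.2.2.1 says "Estimates of the mean differences (Test-Reference) and corresponding 90% CIs will be obtained from the model". SAP 9.4.3 rules out formal hypothesis testing, and Protocol 8.1 reports no power calculation.

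**The concern.** Section 1.2 attaches a conclusion about dose adjustment to stopping. The rule that produces the stop looks only at which side of 2 the point estimate falls, in a comparison of six to eight subjects per group. It takes no account of how precisely the ratio is estimated. An observed GMR of 1.1 and one of 1.9 both stop the trial, and under 1.2 both count as confirmation, although the second may be quite compatible with a doubling of exposure.

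What is at stake is the wording of the trial's main conclusion. The interval that would separate a reassuring result from an inconclusive one will already be computed. The plan does not say how it is to be read.

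**Working it through.** The documents state no power, precision or error rate for this rule, so there is no figure of theirs to reproduce. The precision below is derived from their inputs.

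**Inputs**
- Groups: 8 per group planned, at least 6 evaluable (Protocol 3.1.1).
- Model: ANOVA on log AUC with renal group as the only factor, two-sided 90% CI (Protocol 8.3, SAP 16.2.2.1).
- Variability: 35% CV on clearance (Protocol 1.3.2.1). *Assumption:* AUC in this trial has the same CV. The figure comes from a population PK model in which body weight was a covariate, whereas the ANOVA has none, so a range of 25% to 50% is also shown.

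**Width of the CI**
- Log-SD = √ln(1 + CV²) = √ln(1 + 0.35²) = 0.340.
- SE of the log ratio = SD × √(2/n): 0.340 × √(2/8) = 0.170 for n = 8; 0.340 × √(2/6) = 0.196 for n = 6.
- CI factor = exp(t × SE), with t the 95th percentile on 2n − 2 degrees of freedom: exp(1.761 × 0.170) = 1.35 for n = 8; exp(1.812 × 0.196) = 1.43 for n = 6.
- Example, n = 8, observed GMR 1.90: 1.90 / 1.35 = 1.41 and 1.90 × 1.35 = 2.56.

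**Where the trial stops with a doubling still inside the CI.** The lowest observed GMR whose upper limit reaches 2 is 2 / factor.

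| CV | n = 8 | n = 6 |
|---|---|---|
| 25% | 1.61 | 1.55 |
| 35% | 1.48 | 1.40 |
| 50% | 1.32 | 1.22 |

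Observed values from the tabulated edge up to just below 2 fall in this zone. The edge is exact only if the sample SD equals the assumed one. With 14 degrees of freedom and a true log-SD of 0.340, the 5th to 95th percentiles of the sample SD move it between about 1.63 and 1.35.

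**How often this happens.** Simulation of the two-group log-normal ANOVA, with the variance estimated in each simulated trial, gives the probability that the point estimate is below 2 and the upper 90% limit is 2 or more:

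| True GMR | CV 35%, n = 8 | CV 35%, n = 6 | CV 50%, n = 8 | CV 50%, n = 6 |
|---|---|---|---|---|
| 1.0 | 1% | 5% | 12% | 23% |
| 1.25 | 16% | 27% | 38% | 47% |
| 1.5 | 47% | 54% | 57% | 60% |
| 1.75 | 60% | 60% | 58% | 57% |

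**The case against.** The best defence has four parts.

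*Section 1.2 hands the test to Section 3.* This stands. A reader might infer that 1.2 and 3.1.1 impose opposite burdens of proof. The documents do not support that, because 1.2 refers expressly to the Section 3 criteria: one is a rationale and the other its operating rule. What remains is that the rule cannot deliver the confirmation the rationale attaches to it.

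*No passage says that a GMR below 2 will be reported as no effect.* This also stands. Section 3.1.1 says only that the trial stops, the analysis is descriptive, and the GMR with its CI will be tabulated. A reader might infer that the sponsor has committed to a claim of no effect; neither document contains one. The commitment is narrower: the conclusion in 1.2, with no stated reading of the CI to limit it.

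*The threshold of 2 is supported by a cited paper and by tolerability up to 56.9 mg weekly.* As the protocol presents them, these support the choice of 2 and bear on how much a wrong stop would matter. They do not address the imprecision of an estimate from six to eight subjects per group.

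*No renal effect is expected, because no intact drug was found in urine.* If that is right, the conflict is rare: about 1% with 8 per group and 5% with 6, at 35% CV. It becomes common only if the expectation is wrong, which is the question the trial is run to answer.

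**Conclusion.** The point holds as a mismatch between a conclusion and the test behind it. Followed as written, the plan lets an observed GMR of, say, 1.90 stand as confirmation that no dose-relevant change exists, with a 90% CI of about 1.41 to 2.56. With 35% CV and a sample SD near that assumption, observed GMRs from about 1.5 (n = 8) or 1.4 (n = 6) up to 2 have this property. A zone of this kind exists across the whole 25% to 50% CV range. Its probability depends on the true GMR, which is unknown, and the CV for AUC is an assumption.

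A reader might go further and argue that the trigger itself is wrong, since at a true GMR of 2.0 the trial stops half the time. That does not follow. Any point-estimate trigger at 2 stops about half the time when the truth is 2, and moving the trigger to the CI would be a trade-off: at a true GMR of 1.5, 35% CV and 8 per group, Part 2 would then be run about 52% of the time. Nor would running Part 2 narrow the severe-versus-normal comparison by adding data to it, because it enrols only moderate and mild subjects and reuses the Part 1 controls. The problem lies in what is concluded from stopping, and it can be corrected cheaply.

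**What to change.** Keep the point-estimate trigger of at least 2 for Part 2, and make two wording changes.

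1. In Protocol 1.2, say that not reaching the trigger ends the trial but does not by itself confirm the absence of a relevant PK change. Reword the sentence that follows so that an inconclusive Part 1 does not imply that Part 2 will be run. Without this edit, the second change would contradict 1.2.
2. In Protocol 8.3 and SAP 16.2.2.1, state that the report will claim a two-fold AUC increase is excluded only if the upper 90% limit of the GMR is below 2. If the point estimate is below 2 but the upper limit is 2 or more, the report will state that a two-fold increase was not excluded. Use matching wording in the synopsis, Protocol 3.1.1 and SAP 6.0, and reconcile *may* in 8.3 with *will* elsewhere.

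Using 2 as the bound for the CI is a proposal that borrows the plan's own threshold; the documents use it only as a trigger.

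This needs no extra subjects, procedures or analyses, only edits in six places. The cost is that some trials will be reported as inconclusive even with no true effect: at a true GMR of 1.0, about 1% (n = 8) or 5% (n = 6) with 35% CV, and about 12% or 23% with 50% CV.
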